4 STUDY DESIGN

- Study population and groups: those patients on haemodynamic monitoring in ICU (PiCCO monitoring)
- **Calculation of the sample size:**

Taking into account that the primary objective of the study is to analyze the relationship between the quantitative variables: change in pH and change in Cardiac Contractility, assuming an alpha risk of 5% (95% confidence level), a 20% beta risk (power of 80%) and a minimum ratio that has an estimated clinical significance with a correlation coefficient of 1.5, a bilateral estimate of sample size of 346 subjects is obtained. Assuming a 5% loss (17 individuals) during the study a total of 363 cases would be necessary.

- **Statistical methods:**

The description of quantitative variables is carried out with central tendency and dispersion indices, whether based on values (mean and standard deviation) or on ordinations (median and interquartile range) according to whether they meet normality or not, respectively. Its graphic representation is done with Histograms and Cash Diagrams. The description of categorical variables is performed with absolute and relative frequencies in percentages. Its graphic representation is done with bar charts.

Full title of the research: **The impact of systemic pH on cardiac function and clinical outcome in the critically ill patient.**

IRAS Project ID: **227870**

The relationship between categorical variables is analyzed by comparing proportions with the Pearson Chi-square test, provided that there are less than 20% of squares in the contingency table with expected frequencies less than 5. In the case that there is more 20% of squares with expected frequencies less than 5, the Fisher's exact test is used bilaterally.

The magnitude of the effect of the relationship between two binary variables has been analyzed with the Ratios of proportions or Relative Risk and with the Odds Ratio.

The relationship between a binary exposure variable and a quantitative response is analyzed with the Student-Fisher t test for independent samples if the normality condition is met. According to whether or not the equality of variances are met, the Student-Fisher t test is used for independent groups for homogeneous variances or for non-homogeneous variances, respectively. In case of not fulfilling the condition of normality, the comparison of two means is made with the non-parametric Mann-Whitney U test.

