The relationship between two independent quantitative variables is evaluated with the correlation coefficient r of Pearson if normality is met, or with the nonparametric correlation coefficient ρ of Spearman if normality is not met. Its graphic representation is made with the scatter diagrams or points.

Full title of the research: **The impact of systemic pH on cardiac function and clinical outcome in the critically ill patient.**

IRAS Project ID: **227870**

Normality is assessed with the Kolmogorov-Smirnov test with the Lilliefors significance correction for large samples, or with the Shapiro-Wilks test for small samples. The equality of variances is analyzed with the Levene variance homogeneity test.

The relationship between two related quantitative variables is performed using the Student-Fisher t-test for related samples in case the normality condition is met. Otherwise, the non-parametric Wilcoxon T test is used. The relationship between two paired categorical variables is performed by the McNemar symmetry test.

The relationship between a continuous quantitative response and one or several predictors, whether binary, polytomic or quantitative, is done with Simple or Multiple Linear Regression respectively.

The polytomous predictors variables are introduced in the Linear Regression models broken down into binary indicator variables coded with respect to the first reference category.

An estimative multivariate linear regression model of the effect of the predictor Change of pH (between the lowest and highest pH) on the response Change in cardiac output (corresponding to the moments between the lowest and the highest pH) has been performed. The possible role as confounding factors of several variables on this relationship has been evaluated. A predictive multivariate model of linear regression has been performed to evaluate the factors that intervene in the Cardiac Contractility.

Full title of the research: **The impact of systemic pH on cardiac function and clinical outcome in the critically ill patient.**

IRAS Project ID: **227870**

Both the predictive and the estimative models have been carried out with the manual backward step procedure using the criterion of decreasing statistical significance to establish the order to evaluate the withdrawal or permanence of each predictor.

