In the multivariate predictive linear regression model, the criterion of statistical significance was used to decide the maintenance or withdrawal of the predictors in each step. They remain in the model if they are significant and are removed from the model if they are not significant.

In the multivariate models of linear regression, the criterion of clinical significance has been used to decide on the maintenance or withdrawal of the predictors in each step. They remain in the model if they produce a change greater than 10% in the coefficient of the predictor of interest (presence of confounding bias) and withdraw if the change is less than 10% (absence of confounding bias).

The conditions of application of the simple or multiple linear regression (linearity, independence, normality and equality of variances) are evaluated by analysing the residuals.

Values of $P < 0.05$ are considered significant. The statistical treatment has been performed the statistical package SPSS, version 18 (SPSS Inc, Chicago, IL, USA).

Full title of the research: **The impact of systemic pH on cardiac function and clinical outcome in the critically ill patient.**

IRAS Project ID: **227870**

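### The 10% change-in-coefficient rule often labels outcome predictors unrelated to pH as confounders when the pH effect is absent or very small, so the adjustment set depends on the answer

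*Combined protocol and SAP*

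**What the plan says.** Section 8, Statistical Methods, describes an estimative linear regression of change in cardiac output on change in pH between the lowest and highest pH. Of the covariates it says only: "The possible role as confounding factors of several variables on this relationship has been evaluated". They are neither named nor counted.

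Selection is by manual backward steps, ordered by statistical significance. A variable stays under this rule: "They remain in the model if they produce a change greater than 10% in the coefficient of the predictor of interest (presence of confounding bias"). Otherwise it is to "withdraw if the change is less than 10% (absence of confounding bias"). The sentence refers to multivariate linear models in general. The predictive model has its own P-value rule in the paragraph before, so I read the 10% rule as belonging to the estimative model.

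The same text appears in section 4, Study Design, and in the Study Summary under statistical methodology. None of the three places sets a minimum absolute change, allows for sampling error, or requires that the variable be associated with pH.

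**The concern.** The rule divides the shift in the pH coefficient by the pH coefficient itself. When that coefficient is close to zero, a trivial chance shift exceeds 10% of it. A variable independent of pH change cannot confound the relationship, yet the rule can declare that it does.

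A near-zero slope is a realistic case here. Whether cardiac function changes with pH is the first primary goal in section 3. The hypothesis in the Study Summary is also non-monotonic: in animals, output rises as pH falls from 7.40 to 7.20 and falls below that. A single straight-line slope could therefore be small even if pH matters.

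At stake are the truth of any statement about which variables confound, the stability of the adjustment set, and some precision. When the pH effect is nil, many unrelated predictors are kept. When it is real, most of the same predictors are dropped.

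**Working it through.** **Inputs from section 4.** "assuming an alpha risk of 5% (95% confidence level"); "a 20% beta risk (power of 80"%); two-sided; n = 346 before losses. The effect size is printed as "a minimum ratio that has an estimated clinical significance with a correlation coefficient of 1.5", which no correlation can equal.

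**The plan's own figure.** With the Fisher z formula, n = ((z₀.₉₇₅ + z₀.₈₀)/atanh(r))² + 3. At r = 0.15, n = (2.802/0.1511)² + 3 = 346.6, in line with the stated 346. At r = 1.5, atanh is undefined. I therefore take 0.15 as the effect that fits the sample size. The total also follows: 346 + 17 = 363.

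**Assumptions not in the documents.** All variables are standardised. The candidate Z is independent of pH change, so true confounding is zero. Its standardised association with output is g, taken from 0 to 0.4.

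**Why a larger sample does not help under no effect.** Removing Z shifts the pH coefficient by about g·z₁/√n. The coefficient itself is about √(1−g²)·z₂/√n. Here z₁ and z₂ are independent standard normals. The √n cancels, and the ratio is g/√(1−g²) times a Cauchy variable:

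P(label) = 1 − (2/π)·atan(0.1·√(1−g²)/g)

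This gives 50%, 71%, 80% and 86% for g = 0.1, 0.2, 0.3 and 0.4, whatever n is. For g = 0 the approximation does not apply and the rate must be simulated.

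**Simulated chance that one such variable is labelled a confounder** (n = 346, 200,000 draws per cell):

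| True pH correlation | g = 0 | 0.1 | 0.2 | 0.3 | 0.4 |
|---|---|---|---|---|---|
| 0 | 24% | 46% | 69% | 80% | 85% |
| 0.05 | 17% | 36% | 59% | 72% | 79% |
| 0.15 | 1% | 7% | 21% | 37% | 49% |

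Smaller repeat runs differ by about one point. At n = 363 the no-effect row is the same to within half a point. Under no effect the rate passes 50% at about g = 0.11.

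**Full backward procedure, no pH effect** (n = 346):
- Ten pure-noise candidates: each is kept about 24–25% of the time, and at least one in 71% of studies.
- Five candidates at g = 0.2 plus five noise: kept about 73% and 25% of the time; at least one is kept in 98% of studies.
- Ten candidates at g = 0.2: on average 7.5 of 10 are kept. At a pH correlation of 0.15, about 2 of the same 10 are kept.

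**Effect on the pH test.** Type I error after backward selection stays at about 3–5%. Power at a pH correlation of 0.15, backward rule against all candidates kept (3,000 runs per setting):
- three at g = 0.2: 83% v 86%
- five at g = 0.2: 83% v 87%
- ten at g = 0.1: 80% v 83%
- ten at g = 0.2: about 86% v 94%

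**The case against.** A reader might infer that any variable unrelated to pH will usually be declared a confounder. That is too strong. A variable unrelated to both pH and output is labelled about one time in four under no effect. The majority rate needs a correlation with output above about 0.11 under no effect, and about 0.2 at a pH correlation of 0.05. At 0.15 every rate up to g = 0.4 is below one half.

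A reader might also infer that the primary inference is invalid. It is not. Keeping a pH-independent predictor of output does not in itself bias the pH coefficient, and the type I error is not raised.

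It is fair, too, that none of the four goals in section 3 is to identify confounders. The phrase in brackets may only explain why a covariate is kept, so the documents do not promise a published list of confounders. Section 8 does say that the confounding role of several variables is evaluated, and the rule returns a present or absent verdict for each one. Any such statement inherits the error.

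The power loss depends on assumed candidate sets. Ten independent predictors at 0.2 explain 10 × 0.2² = 40% of the outcome variance, which nothing in the documents supports, and power there still exceeds the planned 80%. This loss arises when the effect is real, so it comes from dropping useful predictors, not from a near-zero denominator.

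What survives is the purely relative rule, the confirmed false-label rates for outcome predictors, and an adjustment set tied to the size of the estimated slope.

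**Conclusion.** The point stands in qualified form. With no pH effect, the rule mislabels a pH-independent predictor of output in about 46–85% of studies for g from 0.1 to 0.4, and a pure-noise variable in about 24%. At a pH correlation of 0.15 the rates run from about 1% to 49% over g from 0 to 0.4. For outcome predictors, enlarging the sample does not cure the no-effect case.

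The consequences are false confounding statements, an adjustment set that depends on the result, and a power loss at a real effect of about 3–4 points in the smaller settings and about 8 in the most extreme. The validity of the pH test is not in question.

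The size rests on assumed values of g, on candidates independent of pH and of each other, and on reading the design correlation as 0.15. Some real candidates will be related to pH, and for those the label may be correct. This should be changed before analysis, but it does not undermine the primary test.

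**What to change.** In section 8, section 4 and the Study Summary, stop using the 10% rule either to select covariates or to declare confounding.

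- Name the adjustment set in advance, on clinical grounds, from pre-exposure items already on the data form (printed under section 20). Examples are admitting diagnosis group, chronic diseases and APACHE II. The form does not say when APACHE II is scored, so confirm that it precedes the pH readings used and consider whether the score itself reflects pH.
- Keep the whole set whatever it does to the pH coefficient.
- Report the unadjusted and adjusted pH coefficients. Report each variable's shift in outcome units per 0.1 pH with a 95% interval (for example by bootstrap), as description only, with no present or absent verdict.

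Replacing 10% of the estimate with 10% of a smallest relevant slope is tempting, but it cannot be done from these documents. The only effect size is an impossible correlation, it was set for contractility and not cardiac output, and no standard deviations are given.

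The cost is wording in three places and no new data. A few more degrees of freedom are used at n = 346. The form lists eleven main diagnosis groups, hence ten indicators, so sparse groups should be pooled in advance. The automatic confounder label is lost.

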8 STATISTICAL METHODS

The description of quantitative variables is carried out with central tendency and dispersion indices, whether based on values (mean and standard deviation) or on ordinations (median and interquartile range) according to whether they meet normality or not, respectively. Its graphic representation is done with Histograms and Cash Diagrams. The description of categorical variables is performed with absolute and relative frequencies in percentages. Its graphic representation is done with bar charts.

The relationship between categorical variables is analyzed by comparing proportions with the Pearson Chi-square test, provided that there are less than 20% of squares in the contingency table with expected frequencies less than 5. In the case that there is more 20% of squares with expected frequencies less than 5, the Fisher's exact test is used bilaterally.

Full title of the research: **The impact of systemic pH on cardiac function and clinical outcome in the critically ill patient.**

IRAS Project ID: **227870**

The magnitude of the effect of the relationship between two binary variables has been analyzed with the Ratios of proportions or Relative Risk and with the Odds Ratio.

The relationship between a binary exposure variable and a quantitative response is analyzed with the Student-Fisher t test for independent samples if the normality condition is met. According to whether or not the equality of variances are met, the Student-Fisher t test is used for independent groups for homogeneous variances or for non-homogeneous variances, respectively. In case of not fulfilling the condition of normality, the comparison of two means is made with the non-parametric Mann-Whitney U test.

The comparison between a polytomic predictor and a quantitative response is made through the analysis of variance (ANOVA) in the case of meeting the conditions of normality and homogeneity of variances. If any of these conditions is not met, it is done with the non-parametric H test of Kruskal-Wallis. If the polytomic predictor is ordinal, the ANOVA trend test or the non-parametric Jonckheere-Terpstra trend test is also used, depending on whether normality is met or not, respectively.

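### The regressions on change in pH have an equal-variance check but no stated action if it fails; HC3 robust standard errors for those slopes would be a cheap improvement

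*Combined protocol and SAP*

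**What the plan says.** Section 8 (Statistical Methods), repeated in the Study Summary and in section 4, plans a linear regression for the "effect of the predictor Change of pH (between the lowest and highest pH) on the response Change in cardiac output", the response being taken between the same two moments. For this and the other regressions, "The conditions of application of the simple or multiple linear regression (linearity, independence, normality and equality of variances) are evaluated by analysing the residuals". The next statement is "Values of $P < 0.05$ are considered significant". No robust standard errors, weighting, transformation or bootstrap is named for a failed check. The software is SPSS 18, and the type of standard error is not given.

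Other methods in the section do have a consequence. For two groups, depending on the variances, "the Student-Fisher t test is used for independent groups for homogeneous variances or for non-homogeneous variances, respectively". For several groups, the ANOVA gives way to Kruskal-Wallis if normality or equal variance fails. For two quantitative variables, Pearson gives way to Spearman, but only when normality fails.

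**The concern.** The predictor is a within-patient range, and the response is a difference that can go either way. The hypothesis in the Study Summary says that underlying cardiac disease and the type of acid-base abnormality might modify the heart's response to pH. If the response per unit of pH differs between patients, the spread of the output change grows with the pH range. Patients with the widest ranges then have both the most leverage on the slope and the noisiest responses. The ordinary standard error does not allow for that and comes out too small.

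At stake are the P-value and confidence interval of the pH slope in the regressions, including the confounder-adjusted one, which no fallback protects. A check with no stated consequence also leaves the response to be chosen after the data have been seen.

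**Working it through.** **1. The plan's own figure.** Section 4 gives two-sided alpha 5%, power 80%, and "with a correlation coefficient of 1.5, a bilateral estimate of sample size of 346 subjects is obtained". A correlation cannot be 1.5, but 0.15 reproduces the number: N = ((1.960 + 0.842)/atanh(0.15))² + 3 = (2.802/0.1511)² + 3 = 346.6. With loss, 346 × 1.05 = 363.3, matching 363. So N = 346 is used below. The misprint is a separate matter.

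**2. Why variance could rise with the range.** Let patient i have output change Y = b·x + e, where x is the pH range, b varies between patients with variance V_b, and e has variance σ². Then Var(Y | x) = x²·V_b + σ², which increases with x whenever V_b > 0.

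**3. Effect on the ordinary standard error.** In large samples, the true variance of the slope divided by the variance that ordinary least squares (OLS) reports is

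R = E[(x − μ)²·v(x)] / (E[(x − μ)²]·E[v(x)]),

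where v(x) is the residual variance at x. A nominal 5% test then runs at 2·(1 − Φ(1.96/√R)).

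*Right-skewed range (assumed).* For a gamma range with shape k (CV = 1/√k) and v(x) proportional to x^m, R = 1 + m(m + 1)/k. With mean 0.20 and SD 0.10, k = 4. The simulated columns have a true slope of zero and n = 346, with 10,000 datasets per setting.

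| Residual SD proportional to | m | R | OLS, formula | OLS, simulated | HC3, simulated |
|---|---|---|---|---|---|
| constant | 0 | 1 | 5.0% | 5.1% | 5.2% |
| range^0.25 | 0.5 | 1.19 | 7.2% | 6.9% | 5.2% |
| range^0.5 | 1 | 1.50 | 11.0% | 11.0% | 5.3% |
| range | 2 | 2.50 | 21.5% | 20.7% | 5.6% |

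*The mechanism in step 2.* Use the same gamma range, slopes averaging zero, and let s be the share of output-change variance due to slope differences. Then R = (1 − s) + 2.5s = 1 + 1.5s.

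| s | R | OLS, formula | OLS, simulated (4,000 datasets) |
|---|---|---|---|
| 10% | 1.15 | 6.8% | 6.3% |
| 25% | 1.375 | 9.5% | 9.5% |
| 50% | 1.75 | 13.8% | 13.9% |
| 75% | 2.125 | 17.9% | 17.2% |

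HC3 gave 5.0-5.6% in these four settings.

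*Evenly spread range (uniform, 0.05 to 0.50).* For SD proportional to range^0.5, symmetry gives R = 1 and 5.0% (simulated 5.0%). For SD proportional to range, with μ = 0.275 and half-width 0.225, R = 1.146 and the rate is 6.7% (simulated 7.1%).

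*Normal range (mean 0.20, SD 0.06), SD proportional to range.* R = (0.04 + 3 × 0.0036)/(0.04 + 0.0036) = 1.165, giving 6.9% (simulated 6.4%).

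**4. The planned correlation in the skewed settings.** The planned Lilliefors test rejected normality of the pH range in 99% (gamma) and 100% (lognormal) of samples, so Spearman would be used. Its false-positive rate was 4.7-6.2% (gamma) and 4.6-6.7% (lognormal) across constant SD and SD proportional to range^0.25, range^0.5 and range.

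**5. Limits.** The simulations are of an unadjusted slope. The same reasoning carries to the adjusted slope, but its size was not simulated. A more skewed gamma range (CV 0.71) with SD proportional to range gave 31.9%, an extreme case. The 5-7% for an even range is for variance that rises with it. With SD falling as range^−0.5, OLS gave 8.4% and HC3 4.8%.

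**The case against.** The strongest reply is that the plan is better protected than it looks. Its only sized analysis is a correlation between change in pH and change in contractility. In the settings where the regression misbehaves, the normality test would send that correlation to Spearman, which stays near 5-7%. This stands. A reader might infer that Pearson shares the weakness, but the documents keep Pearson only when normality holds, and with a normal range the inflation is slight. Spearman, however, gives neither a slope nor an adjusted estimate, so the regressions remain uncovered.

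A reader might also infer that the study's main P-value is far too small. The documents do not support this. The sized response is contractility and the regression response is cardiac output, so which P-value is the main one is not settled. Nor do the documents say that unstable patients have wider pH ranges and wider output swings. They give no SDs, range distribution or variance pattern, and large inflation needs skewness as well as rising variance.

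Ordinary standard errors are inferred from silence. That inference is the natural reading of linear regression in SPSS with nothing else named, but it is still an inference.

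Finally, the Introduction excludes patients with a cardiac history, whereas goal 2 needs them and section 7.2 does not list the exclusion. If they are excluded, one stated source of differing response goes, but the type of acid-base disorder remains.

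**Conclusion.** The point holds in a limited form. The regressions on change in pH have an equal-variance check with no consequence, and no other rule in section 8 covers their slopes. If residual variance rises with a right-skewed pH range, and ordinary standard errors are used, a nominal 5% test of the slope would run at roughly 6-20%. If the range is evenly or normally distributed, it would run at about 5-7%. Everything beyond the textual gap rests on assumed distributions. The stated N of 346 and the planned correlation are not called into question here. This is a cheap improvement, not a defect that undermines the study.

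**What to change.** Add one sentence to section 8, and to its copies in the Study Summary and section 4: the unadjusted and adjusted linear-regression slopes for change in pH are tested, and given 95% confidence intervals, with HC3 robust standard errors, whatever the residual check shows. Keep the planned Pearson/Spearman correlation as it is.

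HC3 changes the standard error and not the coefficient, so the 10% change-in-coefficient rule for confounders works as written. No extra patients or data are needed. The cost is a marginally wider interval if variance is constant (HC3 rejected 4.7-5.2% in the constant-variance runs) and a macro or script if the software lacks the option. HC3 does not restore precision. If the ordinary standard error were understated by a factor of 1.2 (true alpha about 10%), power at r = 0.15 with a correct standard error would be about 65% instead of 80%.

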2 BACKGROUND AND RATIONALE

3 OBJECTIVES

Goals

Primary

1. Assess whether there are significant changes in cardiac function associated with changes in blood pH.
2. Relate the changes in cardiac function to presence or absence of underlying cardiac disease.

Secondary

3. To establish which factors affected by blood pH have an impact on cardiac function.

Full title of the research: **The impact of systemic pH on cardiac function and clinical outcome in the critically ill patient.**

IRAS Project ID: **227870**

4. Study the mortality of patients admitted to the Intensive Care Unit (ICU) who had continuous cardiac monitoring at any time during their admission and relate it to changes in blood pH.

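### Two primary goals, no named primary measure and no order of testing: the 5% alpha behind the sample size does not cover the primary claim

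*Combined protocol and SAP*

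**What the plan says.** Section 3 (Objectives) and the Study Summary list two goals as primary. The first is "Assess whether there are significant changes in cardiac function associated with changes in blood pH". The second is "Relate the changes in cardiac function to presence or absence of underlying cardiac disease". Neither says which measure stands for cardiac function.

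The sample-size paragraph in section 4 (Study Design) speaks of a single primary objective, the relationship between "change in pH and change in Cardiac Contractility". It assumes 5% alpha and 80% power for that one relationship, and states that "a bilateral estimate of sample size of 346 subjects is obtained".

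Section 8 (Statistical Methods) describes two multivariable regressions. One estimates the effect of change in pH on change in cardiac output. The other is a predictive model of the factors that influence contractility. The significance rule is "Values of $P < 0.05$ are considered significant". The same statistical text appears in the Study Summary and in section 4. None of the three copies gives an order of testing, a split of alpha, a correction, or a definition of a positive primary result.

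**The concern.** A study sized on one test at 5% carries a 5% risk of a false primary claim only if that one test decides the claim. Here two goals have primary status, the measure is open, and the sized outcome (contractility) differs from the outcome of the effect model (cardiac output). A significant result for either goal, or on either measure under goal 1, could be reported as meeting a primary goal.

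Two things are at stake. The stated alpha would understate the risk of a false primary finding. And a reader of the report could not tell whether a positive result was the planned one or the better of several. Section 1 says the results should help clinicians understand how best to treat these patients, so a positive primary finding is likely to be read as firm.

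**Working it through.** **Inputs from the documents.** Two primary goals (section 3). Two-sided alpha 5%, power 80%, 346 evaluable, 5% loss, 363 in total (section 4). Threshold 0.05 for every test (section 8). Measures named: contractility (section 4 sizing; section 8 predictive model) and cardiac output (section 8 effect model).

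**Assumptions.** The correlation between test statistics is not given, so I show 0 to 0.9. The effect size is printed as "a minimum ratio that has an estimated clinical significance with a correlation coefficient of 1.5". A correlation cannot exceed 1, so I read it as 0.15.

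**Step 1: the plan's own figure.** Fisher z for one correlation:

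n = ((z for alpha/2 + z for power) / atanh(r))² + 3 = ((1.960 + 0.842) / 0.1511)² + 3 = 346.6.

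This matches 346. A one-sided test would give 274, which does not. For losses, 346 × 0.05 = 17.3, and 346 + 17 = 363, in line with "Assuming a 5% loss (17 individuals) during the study a total of 363 cases would be necessary". The sizing therefore covers exactly one two-sided test at 5%.

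**Step 2: which tests the text supports.** It supports about two, reached in either of two ways:
- one test for each primary goal; or
- goal 1 alone, on contractility (the sized relationship) and on cardiac output (the modelled one).

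Testing both measures for both goals would make four. The plan does not set this out, so I treat it as an upper scenario.

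**Step 3: chance of at least one false positive, each test at 5%, no true effects.** If independent:
- two tests: 1 − 0.95² = 9.75%
- four tests: 1 − 0.95⁴ = 18.5%

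For correlated tests, by simulation of equally correlated two-sided z statistics (1,000,000 draws):

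| Correlation | Two tests | Four tests (upper scenario) |
|---|---|---|
| 0.3 | 9.5% | 17.4% |
| 0.5 | 9.1% | 15.6% |
| 0.7 | 8.4% | 13.1% |
| 0.9 | 7.0% | 9.4% |

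Three tests (goal 1 on both measures, plus one for goal 2) would give 1 − 0.95³ = 14.3% if independent.

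**Step 4: power under each remedy, r read as 0.15, n = 346.**
- First test of a fixed order, at 5%: 0.1511 × √343 − 1.960 = 0.839, which gives 79.9%.
- Bonferroni over two tests, at 2.5% each: 0.1511 × √343 − 2.241 = 0.558, which gives 71.1%. Holding 80% would need 420 evaluable, or 443 after dividing by 0.95 for losses.

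A fixed order holds the family error at 5% because the first true null hypothesis in the sequence is rejected with probability at most 5%, and later ones are tested only after that.

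**The case against.** The strongest reply is that section 4 does name one primary objective. If pH against contractility alone were declared confirmatory, 5% would hold. That is correct. But section 3 gives a second goal equal standing, the effect model in section 8 uses a different outcome, and nothing says which governs.

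A reader might infer a family of at least four primary tests and quote 18.5% as the error rate. The documents do not support that. They specify no test of goal 2 for either measure. The contractility regression is called predictive and fits secondary goal 3 at least as well as a primary goal. Both measures come from the same monitored patients, so independence is the extreme case. Nor does the text support a larger count based on further PiCCO indices, because the statistical section names none as an outcome.

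Goal 2 may not be testable at all. Section 1 excludes patients with cardiac history, although section 7.2 does not list that exclusion and the data form in section 20 records ischaemic heart disease and heart failure. This stands, and it bears on both the count and the fix. If goal 2 dropped out, the two measures under goal 1 would still leave two uncorrected tests.

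Finally, the study is observational and its goals ask different questions, so family-wise control is partly a matter of judgement. That lowers the weight of the point but does not remove it: the plan states an alpha, a power and a significance rule, and they should refer to the same claim.

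**Conclusion.** The point holds in a limited form. The 5% used for sizing does not apply to the primary claim as the plan is written. For the two tests that the text supports, the risk of at least one false positive is about 7% to 10%. About 9% to 18.5% is an upper scenario, reached only if both measures were tested for both goals.

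These figures assume no true effects, each test at 0.05, and a correlation between tests of 0.9 to 0, which the documents do not give. They leave out any further inflation from letting the data choose between Pearson and Spearman, or from backward selection. The power figures rest on reading the printed 1.5 as 0.15. The consequence is an overstated primary finding in an observational study. It should be corrected in the text and does not put the design itself in doubt.

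**What to change.** In the sample-size paragraph of section 4 and in section 8, with the repeated text in the Study Summary brought into line:

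1. Name change in pH against change in contractility, the relationship the study is sized on, as the single first primary test at two-sided 5%. State its method in advance (Pearson, Spearman or an adjusted regression). If an adjusted regression is meant, its model has to be written, because the plan gives an effect model only for cardiac output.
2. Test change in cardiac output at 5% only if the first test is significant.
3. Test goal 2, on a named measure with a named test, at 5% only if the second is significant. Before goal 2 is kept in the sequence, reconcile it with the exclusion of patients with cardiac history in section 1.
4. Where the sequence stops, report the remaining results as estimates with 95% confidence intervals and make no primary claim.

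The secondary goals need not be relabelled for this purpose.

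The cost is wording, plus a model specification if step 1 is to be adjusted. Recruitment does not change, and an unadjusted first test keeps its planned power (79.9% at 346, on the 0.15 reading). The downside is that cardiac output and goal 2 cannot be claimed as primary findings if the first test fails. This matters because the animal evidence behind the hypothesis in the Study Summary concerns cardiac output. If the investigators would rather put cardiac output first, they should say so before analysis and base the sample size on it.
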